4.1.3 Safety and Response Assessment Visit (Day 28 ± 3 days)

During the visit, the following assessment must be completed:

1. Medical history for adverse events
2. Vital signs including pulse oximetry, weight and physical exam including brief neurological exam
3. ECOG performance status
4. Concomitant medications
5. Complete blood count, differential
6. Chemistry panel (Glucose, Ca, Mg, Phos, Albumin, Total Protein, Total Bilirubin, K, Na, Cl, HCO₃, BUN, Cr, ALT, AST, lactate dehydrogenase)
7. Urinalysis

8. Urine pregnancy test for all women of child-bearing potential
9. CRP, ferritin
10. Research blood (See Laboratory Manual for collection details)
11. If present at baseline, serum protein electrophoresis (SPEP), serum immunofixation electrophoresis (SIFE)
12. If present at baseline, 24-h urine for total protein, urine protein electrophoresis (UPEP), urine immunofixation electrophoresis (UIFE)
13. If present at baseline, serum free light chain (FLC) assay
14. β 2- microglobulin
15. If required for depth-of-response evaluation based on peripheral markers, then unilateral bone marrow aspirate + biopsy, including bone marrow immunohistochemistry and bone marrow flow cytometry. MRD assessment (with NGS) is performed if patient is in sCR.
16. Imaging of a previously known plasmacytoma if already imaged at baseline visit

4.1.4 Follow-up Months 1, 3, 6, 9, 12, 18, 24, 36 (\pm 2 weeks)

1. Medical history for adverse events
2. Current medical conditions and physical examination (including weight, vital signs, pulse oximetry)
3. ECOG performance status
4. Concomitant medications
5. Complete blood count, differential
6. Chemistry panel (Glucose, Ca, Mg, Phos, Albumin, Total Protein, Total Bilirubin, K, Na, Cl, HCO₃, BUN, Cr, ALT, AST, lactate dehydrogenase)
7. Urinalysis
8. If present at baseline, serum protein electrophoresis (SPEP), serum immunofixation electrophoresis (SIFE)
9. If present at baseline, 24-h urine for total protein, urine protein electrophoresis (UPEP), urine immunofixation electrophoresis (UIFE)
10. If present at baseline, serum free light chain (FLC) assay
11. β 2- microglobulin

Additional notes:

- If required for depth-of-response evaluation based on peripheral markers, then unilateral bone marrow aspirate + biopsy, including bone marrow immunohistochemistry and bone marrow flow cytometry. MRD assessment (with NGS) is performed if patient is in sCR.
- Imaging of a previously known plasmacytoma if already imaged at baseline visit
- Research Blood (See Laboratory Manual for collection details)

4.2 Study Calendar

	Screening	Descartes-11 Infusion							Response Assessment	Follow-Up
Procedures	Day -60 to Day 0	Day 1	Day 4	Day 8	Day 11	Day 15	Day 18	Day 28	Months 1,3,6,9,12,18,24,36	
Informed consent										
Eligibility	X									
Demographics										
Physical exam	X	X	X	X	X	X	X	X	X	
Performance Score	X	X	X	X	X	X	X	X	X	
Vital Signs, O ₂ saturation	X	X	X	X	X	X	X	X	X	
Height	X									
Weight	X								X	
Serious Adverse Events		X	X	X	X	X	X	X		
Adverse events		X	X	X	X	X	X	X	X	
Concomitant Medications	X	X	X	X	X	X	X	X	X	
Descartes-11		X	X	X	X	X	X			
CBC w/ differential	X	X		X		X		X		
Chemistry ^a	X	X		X		X		X		
PT/INR, PTT	X									
CRP, ferritin	X	X								
Urinalysis	X	X		X		X		X		
β-HCG ^b	X							X		
Urine pregnancy test ^b		X	X	X	X	X	X			
Lymphocyte subset counts ^c	X									
Serum FLC ratio	X	X ^g						X	X	

	Screening	Descartes-11 Infusion							Response Assessment	Follow-Up
Procedures	Day -60 to Day 0	Day 1	Day 4	Day 8	Day 11	Day 15	Day 18	Day 28	Months 1,3,6,9,12,18,24,36	
Serum electrophoresis and immunofixation	X	X ^g						X	X	
β ₂ -microglobulin	X							X	X	
24-hour urine for electrophoresis and immunofixation	X	X ^g						X	X	
Bone marrow biopsy and aspiration	X							X ⁱ	X ⁱ	
Research Blood ^d	X	X	X	X	X	X	X			
ECG	X									
Echocardiogram ^h	X									
Imaging	X ^f							X ^j	X ^j	
Infectious Disease panel ^e	X									

^a Chemistry includes Glucose, Ca, Mg, Phos, ALP, Albumin, Total protein, Total bilirubin, K, Na, Cl, HCO₃, BUN, Uric acid, Cr, ALT, AST, LDH

^b Child-bearing women only

^c Lymphocyte subset includes CD19+, CD3+, CD4+, CD8+, CD56+ cells

^d Details of Research Blood collection is explained in Laboratory Manual.

^e Infectious Disease panel includes Hep B surface antigen, Hep B core total antibody. Hep C Virus Ab, HIV-1/HIV-2

^f ONLY if there is known plasmacytoma at baseline.

^g One of these should be done if not performed within the past 7 days

^h If not done in the previous 6 months.

ⁱ Bone marrow aspiration and biopsy tests will be performed ONLY if needed for depth-of-response or relapse evaluation.

^j ONLY if there is known plasmacytoma at baseline and is required for evaluating depth of response based on IMWG criteria ([Table 1](#)).

4.3 Biospecimen Collection for Exploratory Studies

4.3.1 Explanation of Research Blood Assays

4.3.1.1 Direct Measurement of Circulating Descartes-11 Cells

[REDACTED]

4.3.1.2 Serum Biomarkers related to CRS

[REDACTED]

4.3.1.3 Additional Assays

[REDACTED]

4.3.2 Future Studies

With patient informed consent, blood and tissue specimens collected during this research project may be banked and used in the future to investigate new scientific questions related to this study. However, this research may only be done if the risks of the new questions were covered in the consent document. If new risks are associated with the research, a protocol amendment will be

required, and informed consent will be obtained from all research subjects to whom these new studies and risks pertain.

4.3.3 Research Blood Sample and Remaining Study Drug Destruction Upon Protocol Completion

Any remaining frozen study drug after completing treatment should be returned to Sponsor. Research blood samples, and associated data, can only be permanently archived if the subject has provided informed consent for future use. If researchers have samples remaining once they have completed all studies associated with the protocol, they must be returned to Sponsor.

The principal investigators will contact Sponsor if samples become unsalvageable because of environmental factors (ex. broken freezer or lack of dry ice in a shipping container) or if a patient withdraws consent. Samples will also be reported as lost if they are lost in transit between facilities or misplaced by a researcher.

4.4 Treatment Response Assessment

IMWG response criteria published in 2016 will be used for response assessment. Below is a table summarizing the parameter to stratify a response.

Table 1. IMWG Response Criteria⁶⁸

Response Category	Parameters
Stringent complete response	Complete response as defined below plus normal FLC ratio and absence of clonal cells in bone marrow biopsy by immunohistochemistry (Kappa/Lambda \leq 4:1 or \geq 1:2) or kappa and lambda patients, respectively, after counting \geq 100 plasma cells
Complete response	Negative immunofixation on the serum and urine and disappearance of any soft tissue plasmacytomas and $<5\%$ plasma cells in bone marrow aspirates
Very good partial response	Serum and M-protein detectable by immunofixation but not on electrophoresis or $\geq 90\%$ reduction in M-protein plus urine M-protein level <100 mg/24 hours
Partial response	$\geq 50\%$ reduction of serum M-protein plus reduction in 24 hours urinary M-protein by $\geq 90\%$ or to <200 mg/24 hours. If the serum and urine M-protein are unmeasurable, a $\geq 50\%$ decrease in the difference between involved and uninvolved FLC levels is required in place of the M-protein criteria. If the serum and urine M-protein as well as serum-free light chains are unmeasurable, $\geq 50\%$ reduction in plasma cells is required, provided baseline bone marrow plasma-cell percentage was $\geq 30\%$. In addition to these criteria, if present at baseline, $\geq 50\%$ reduction in size (sum of the products of the maximum perpendicular diameters (SPD) of measured lesions) of soft tissue plasmacytomas is also required.
Minimal response	$\geq 25\%$ but $\leq 49\%$ reduction of serum M-protein and reduction in urine M-protein by 50-89%. In addition to these criteria, if present at baseline, $\geq 50\%$ reduction in size (sum of the products of the maximum perpendicular diameters of measured lesions) of soft tissue plasmacytomas is also required.

Response Category	Parameters
Progressive disease	
Any one or more of the following criteria:
 
Increase of 25% from lowest confirmed response value in one or more of the following criteria:
 
 • Serum M-protein (absolute increase must be ≥ 0.5 g/dL) • Serum M-protein increase ≥ 1 g/dL, if the lowest M component was ≥ 5 g/dL • Urine M-protein (absolute increase must be ≥ 200 mg/24 h) • In patients without measurable serum and urine M-protein levels, the difference between involved and uninvolved FLC levels (absolute increase must be >10 mg/dL) • In patients without measurable serum and urine M-protein levels and without measurable involved FLC levels, bone marrow plasma-cell percentage irrespective of baseline status (absolute increase must be $\geq 10\%$) • Appearance of a new lesion(s), $\geq 50\%$ increase from nadir in SPD of >1 lesion, or $\geq 50\%$ increase in the longest diameter of a previous lesion >1 cm in short axis • $\geq 50\%$ increase in circulating plasma cells (minimum of 200 cells per μL) if this is the only measure of disease

To investigate disease-free survival, the following relapse criteria will be used.

Table 2. Relapse from sCR or MRD-negative Criteria

Relapse from complete response	
Any of the following criteria:
 
 • Reappearance of serum or urine M-protein by immunofixation or electrophoresis • Development of $\geq 5\%$ plasma cells in the bone marrow • Appearance of any other sign of progression (i.e., new plasmacytoma, lytic bone lesion, or hypercalcemia)
Relapse from MRD-negative complete response	
Any one or more of the following criteria:
 
 • Loss of MRD negative state (evidence of clonal plasma cells on NGF or NGS, or positive imaging study for recurrence of myeloma) • Reappearance of serum or urine M-protein by immunofixation or electrophoresis • Development of $\geq 5\%$ clonal plasma cells in the bone marrow; Appearance of any other sign of progression (i.e., new plasmacytoma, lytic bone lesion, or hypercalcemia)

4.5 Criteria for Removal from Protocol Therapy and Off-Study Criteria

4.5.1 Criteria for Removal from Descartes-11 Therapy

Off-treatment criteria mainly apply to eligibility for potential repeat Descartes-11 treatments. Completion of each cycle includes a response assessment visit. Patients will be taken off treatment for the following:

- General or specific changes in the patient's condition render the patient unacceptable for further treatment on this study in the judgment of the investigator.
- Any Descartes-11-related Grade 3 to 5 toxicity occurring within the 14 days immediately after infusion of the drug product, with the following exceptions:
 - \leq Grade 3 to 4 Tumor Lysis Syndrome (TLS) lasting <7 days
 - Grade 2 CRS associated with fever, hypotension or hypoxia lasting less than 72 hours (i.e., improves to \leq Grade 1 CRS in less than 72 hours)
 - Non-hematologic toxicities:
 - Fever of any grade, including febrile neutropenia
 - \leq Grade 3 diarrhea lasting <72 hours
 - \leq Grade 3 nausea and/or vomiting lasting <72 hours
 - \leq Grade 3 fatigue lasting <7 days
 - \leq Grade 4 transaminase, bilirubin, blood urea nitrogen (BUN), or creatinine elevation lasting <7 days
 - Hematologic toxicities:
 - \leq Grade 3 neutropenia of any duration or Grade 4 neutropenia lasting <28 days
 - \leq Grade 3 anemia of any duration or Grade 4 anemia lasting <28 days
 - \leq Grade 3 thrombocytopenia of any duration or Grade 4 thrombocytopenia lasting <28 days
 - All cytopenias except neutropenia, anemia, and thrombocytopenia as described above

The National Cancer Institute Common Terminology Criteria for Adverse Events (NCI CTCAE) Version 5 will be used to grade toxicities during the trial unless specified above.

4.5.2 Criteria for Off-Study

Patients will be taken off study for the following:

- The patient voluntarily withdraws
- There is significant patient noncompliance
- Death
- Development of progressive or relapsed MM after completing Descartes-11 infusions

Patients must be followed until all adverse events have resolved to grade 2 or less other than lymphopenia or alopecia. If an adverse event is not expected to resolve to Grade 2 or less, this will be noted in the patient medical record and the patient will be taken off-study. Patients, upon obtaining consent, will also be followed for additional clinical outcomes like overall survival.

5 Safety, Adverse Events, Protocol Deviation and Stopping Rules

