3.2.1 Overall Treatment Design

The overall schedule of treatment for this Phase II study is illustrated in [Figure 1](#). Steps shown prior to Screening affect eligibility but are not part of the study.

Eligible patients will receive an induction regimen with at least 2 anti-myeloma agents excluding monoclonal antibodies. After completion of the full pre-transplant induction regimen prior to high-dose chemotherapy and ASCT, eligible patients must have measurable residual disease as defined in the Eligibility Criteria. A patient can be screened and enrolled at that point.

Descartes-11 treatment will begin at least 7 days after the patient's final dose of anti-myeloma therapy. The dose of cells will be 25×10^6 cells/kg, and doses will be given on Days 1, 4, 8, 11, 15, 18 (i.e., total dose of 150×10^6 cells/kg). Weight obtained during Screening Visit will be used for dose calculation. Doses are expressed as the number of live CAR+ cells.

After completing all cell infusions, the patient will be evaluated for clinical response and then followed-up for up to 36 months unless they meet off-study criteria outlined in [Section 4.5.2](#). During the follow-up period, if indicated, any additional induction therapy, high-dose chemotherapy and/or ASCT may be administered at the discretion of the investigator. Except for experimental agents that are not approved for myeloma treatment, treatment will be left to the investigator's discretion. The patient will be followed every 3 months for the first year, every 6 months for the second year and one time during the third year.

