5.1 Definitions

5.1.1 Adverse Events (AE)

An adverse event (AE) is defined as any reaction, side effect, or untoward event that occurs during the clinical trial associated with the use of a test article in humans, whether or not the event is considered related to the treatment or clinically significant. For this study, AEs will include events reported by the patient, as well as clinically significant abnormal findings on physical examination or laboratory evaluation. A new illness, symptom, sign or worsening of a pre-existing condition or abnormality is considered an AE. An abnormal laboratory value will be considered an AE if the laboratory abnormality is characterized by any of the following:

- Results in discontinuation from the study
- Is associated with clinical signs or symptoms
- Requires treatment or any other therapeutic intervention
- Is associated with death or another serious adverse event, including hospitalization.
- Is judged by the Investigator to be of significant clinical impact

All AEs, including clinically significant abnormal findings on laboratory evaluations, regardless of severity, will be followed until satisfactory resolution.

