5.2 Recording of Adverse Events

5.2.1 Adverse Event Recording Period

The study period during which adverse events must be reported is normally defined as the period from the initiation of any study procedures to the protocol therapy completion. For this study, collection of adverse events will begin with enrollment until the subject is off-study. Serious Adverse Event reporting period starts with leukapheresis and ends at 30 days after last Descartes-11 infusion.

All unresolved adverse events should be followed by the investigator until the events are resolved, the subject is lost to follow-up, or the adverse event is otherwise explained. At the last scheduled visit, the investigator should instruct each subject to report any suspected adverse event(s) that might reasonably be related to participation in this study. The investigator should notify the Sponsor of any death or adverse event occurring at any time after a subject has discontinued or terminated study participation if the event may reasonably be related to this study. The Sponsor should also be notified if the investigator should become aware of the development of cancer or of a congenital anomaly in a subsequently conceived offspring of a subject that has participated in this study.

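### Section 4.5.2 as written takes patients with lasting Grade 3-4 adverse events off study, so routine collection of new events and scheduled response follow-up end because of toxicity

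*Combined protocol and SAP*

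**What the plan says.** Section 4.5.2 lists four reasons for going off study: voluntary withdrawal, significant noncompliance, death, and progression or relapse after the infusions. Two sentences follow the list. The first sets a duty: "Patients must be followed until all adverse events have resolved to grade 2 or less other than lymphopenia or alopecia". The second deals with events that will not get there, and its instruction is: "this will be noted in the patient medical record and the patient will be taken off-study". A last sentence allows consented follow-up for further outcomes, with overall survival as the example.

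Two other sections give off-study status its effect:
- Section 5.2.1: "collection of adverse events will begin with enrollment until the subject is off-study".
- Section 3.2.1: patients are evaluated for response and then "followed-up for up to 36 months unless they meet off-study criteria", with a direct reference to Section 4.5.2.

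Other provisions bear on what happens to the event itself and to later events:
- Section 5.1.1: all adverse events, "regardless of severity, will be followed until satisfactory resolution".
- Section 5.2.1: "All unresolved adverse events should be followed by the investigator until the events are resolved, the subject is lost to follow-up", or until the event is explained in some other way.
- Section 5.2.4 lets follow-up of an event close at stabilization, when study treatment or participation is found not to be the cause, or when the event is judged permanent.
- Section 5.2.1, on serious events: "Serious Adverse Event reporting period starts with leukapheresis and ends at 30 days after last Descartes-11 infusion". It also asks the investigator to tell the sponsor of deaths or adverse events after participation ends, if they may reasonably be related to the study.

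**The concern.** The rule makes leaving the study depend on having severe toxicity that does not go away. In a single-arm trial of a cell product presented as having limited toxicity, these are the patients whose later course matters most to the safety profile. If they leave routine collection, the adverse-event tables for the 36 months under-represent what happens after a lasting severe event.

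The efficacy side has the same problem. Section 3.4 says the follow-up period serves the secondary objectives, and Section 4.4 sets relapse criteria for studying disease-free survival. A patient removed for toxicity while still in response stops being assessed at that point. Treating that as ordinary censoring assumes that lasting toxicity is unrelated to later relapse, and nothing in the plan supports this.

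**Working it through.** The plan states no figure on this point, so the check traces what the rule sets off and what could reverse it.

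**1. What triggers the rule.** An ongoing event not expected to reach Grade 2 or less is a Grade 3 or 4 event. Section 4.5.2 sets no time window and no causality requirement, and Section 5.1.1 counts adverse events whether or not they are related. Sections 3.2.1 and 3.4 allow further anti-myeloma therapy, including high-dose chemotherapy and transplant, during follow-up. A lasting Grade 3-4 event from that later therapy therefore meets the trigger too. Lymphopenia and alopecia are excepted in the preceding sentence; whether the exception carries over is not said.

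**2. What off-study status ends.** Under Section 5.2.1 it ends routine adverse-event collection. Under Section 3.2.1 it ends the scheduled follow-up, whose visits in Section 4.1.4 carry the adverse-event history, the myeloma markers and, where needed, marrow and MRD assessment.

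**3. What could restore it.**
- The consented follow-up in Section 4.5.2 is described for outcomes such as survival, not for response visits or adverse events.
- The one-year data collection in Section 2.2.5 is for early withdrawals. Section 2.2.4 treats as premature discontinuation only patients without one completed infusion, so 2.2.5 does not clearly reach treated patients.
- The serious-event window is fixed, and off-study status does not clearly shorten it. With the last infusion on Day 18 it runs to Day 18 + 30 = Day 48. From then to Month 36, routine adverse-event collection is the only systematic capture, and that is what off-study status stops.
- Notification after participation ends covers only events that may reasonably be related.

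**4. Net effect for a treated patient removed under this sentence.**
- *Kept:* follow-up of the lasting event (5.1.1, 5.2.1, subject to the closing rules in 5.2.4); serious-event reporting to 30 days after the last infusion; notice of later related events; survival, with consent.
- *Lost:* routine collection of new adverse events, and scheduled response and relapse assessment.

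**5. Size per patient.** Section 4.1.4 schedules 8 follow-up visits (Months 1, 3, 6, 9, 12, 18, 24 and 36). Removal just after Day 28 loses all 8; removal after the Month 12 visit loses 3 (Months 18, 24 and 36). With the planned sample of 34, each such patient is 1/34 = 2.9% of the trial. The documents give no rate of lasting Grade 3-4 events, so no total follows.

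**The case against.** The best defence is that the sentence was never meant to remove anyone. It stands after the four listed reasons and directly after an open-ended duty to follow events down to Grade 2. It may only release patients who are already leaving from a duty that could never be met. That reading is possible. But the sentence says without condition that the patient leaves the study, it sits under the off-study heading, and Section 3.2.1 sends the reader there to learn when follow-up stops. A site could reasonably apply it literally.

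A second defence is that the closing rules for events are not uniform in any case. Section 5.2.4 accepts stabilization or a judgement of permanence, so closing an event that will not resolve is not out of line with the rest of the protocol. That stands. It shows, however, that an event can be closed without removing the patient, which is the distinction Section 4.5.2 fails to make.

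Third, a reader might infer that the Day 28 primary endpoint is lost for a patient whose event is judged irreversible during the infusion period. The documents do not support this firmly. In Section 3.2.1 the off-study condition most naturally limits the follow-up that comes after the response evaluation. Section 4.5.1 handles early related Grade 3-5 toxicity as removal from treatment, which is separate from off-study status. No passage cancels the Day 28 visit.

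Fourth, few patients may be affected: Section 3.3.4 reports no cytokine release syndrome or neurotoxicity with this product so far. That is fair for those two toxicities, but the trigger covers any cause.

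**Conclusion.** The point stands as a wording fault with a real consequence. Read as written, Section 4.5.2 removes patients from routine collection of new adverse events and from scheduled response and relapse assessment because they have lasting Grade 3-4 toxicity, and no other provision clearly restores either for treated patients. The loss is up to eight visits per affected patient, each patient being 2.9% of the planned 34.

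This rests on the literal reading. The effect on any given secondary analysis is not known: the secondary objectives are not legible in the copy reviewed, and Section 6 leaves the analysis to a separate SAP whose text was not available here.

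Two stronger conclusions should not be drawn. A reader might infer that the severe events themselves are cut short or that serious events go unreported; Sections 5.1.1 and 5.2.1 still require follow-up of the unresolved event and keep the serious-event window. A reader might also put a percentage on the share of patients lost; the documents offer no basis for one. The matter should be corrected, but it does not by itself put the primary analysis in doubt.

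**What to change.** Separate the end of follow-up for an event from the end of study participation.

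- In Section 4.5.2, delete the clause that takes the patient off study. In its place say that an event not expected to reach Grade 2 or less is recorded as permanent or ongoing, and that the patient stays on study for adverse-event collection, the Day 28 assessment and scheduled follow-up unless one of the four listed reasons applies.
- Reconcile that text with Sections 3.2.1, 5.1.1, 5.2.1 and 5.2.4, so that one stated rule says when follow-up of a single event may close.

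If the sponsor meant only to release patients who were already leaving, the same edit makes that plain. It is a wording amendment on data collection and changes no dose or treatment rule. The cost is that already scheduled visits are kept for a few patients.
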